## Cover

**Official Title of Study**: Prevention of Pressure Injuries During Aeromedical Evacuation or Prolonged Field Care

#NCT03924622

Date: 4 Jan 2019

Statistical Analysis Plan This study proposes to compare the effect of presence or absence of a Mepilex dressing) on variables (IL- $1\alpha$ /TP, TcPO2, interface pressure, skin temperature and moisture) potentially reflecting the modified effects of pressure, shear and microclimate associated with lying for an interval of (120 minutes) on either a standard NATO litter with mattress or a VSB. Primary analyses will contrast the Mepilex and non-Mepilex dressing groups, WITHIN the two support platform strata. That is, the two contrasts LITTER + Mattress (Mepilex vs. not) and VSB (Mepilex vs. not) will be the analysis foci. Analyses of the effect of support platform, and the interactions of platform with presence/absence of Mepilex pad will be considered secondary and exploratory. The statistical tests will be based on a group (Mepilex vs. non-Mepilex) by time (first sample – unloaded baseline, second sample post 120-minute loading) analysis. Analysis options depending on data structure include a repeated measures Group x Time ANOVA, an ANCOVA-based group analysis of the post-loading measurement controlled for the preloading measurement, a group analysis of the simple change score (post-loading – preloading), and a longitudinal analysis of the two-time points by group using Generalized Estimating Equations or a Linear Mixed Models. It is important to note that several of the studies using IL-1 $\alpha$  as a dependent variable have used non-parametric statistical tests. Similarly, error bar plots in published papers document a degree of heteroscedasticity, with the variability in a batch apparently having considerable dependence on its mean. This potential non-normality problem may be met with data transformation (e.g., square root or logarithmic transform) to an appropriate carrier or use of Generalized Linear Models with an appropriate non-linear monotonic link function, or the use of non-parametric statistics. As an example of application of the last method to the current data structures, the simple change score or residual change score from pre- to post- loading could be analyzed with the non-parametric Mann-Whitney U test. Power Analysis: The a priori justification of group sample size with respect to statistical power will be based on the potential change in the variable (IL- $1\alpha$ /Total ratio), which is measured in each participant immediately before and after lying for 120 minutes on the support platform. The analyses of other variables (e.g., TCPO2, interface pressure, skin temperature/moisture) will be treated as descriptive and secondary. When there is limited evidence in the literature that bear directly on the estimation of an effect size in planning a preliminary study, several authors and agencies have argued for setting the sample size per group N per group = 12.76-78 Assuming two tailed two independent group comparisons, with an adjusted significance threshold set to alpha = 0.025 to accommodate multiple testing at the alpha = 0.05 level for both the NATO litter and the "VSB" strata, and the size of each group N = 12, the minimum Cohen's d effect size per test necessary to achieve statistical power P = 0.80 is d = 1.336, which is considered a very large and ambitious effect size. However, there is related support in the literature that this level of effect is achievable using the proposed protocol. Hemmes55 (see Fig. 3, page 86, and Table A1, page 88) demonstrated that lying on either a rigid or soft-layered spineboard for 60 minutes raised mean sacral IL- $1\alpha$ /TP ratio by more than a factor of 10. de Wert24 (see Fig. 4A, page 510), using a 30- minute pressure and shear loading protocol on the forearm, showed that the presence of a Mepilex dressing resulted in IL-1 $\alpha$ /TP ratio levels that were on the order of 7 times smaller than the "no dressing" condition.

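### The SAP allows GEE, mixed models and non-linear-link GLMs for the two 12-versus-12 primary contrasts without a small-sample inference rule; run with large-sample inference, they exceed the stated 0.025

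*SAP*

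**What the plan says.** The SAP makes two comparisons primary: "the two contrasts LITTER + Mattress (Mepilex vs. not) and VSB (Mepilex vs. not) will be the analysis foci". Each is a group-by-time question with one unloaded and one post-loading measurement. The method is left to depend on data structure. The list includes repeated-measures ANOVA, ANCOVA, a change-score comparison and "a longitudinal analysis of the two-time points by group using Generalized Estimating Equations or a Linear Mixed Models". Because IL-1α/TP is expected to be non-normal with variance that depends on the mean, the SAP adds transformation, "use of Generalized Linear Models with an appropriate non-linear monotonic link function", and non-parametric tests.

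The error rate is set in the Power Analysis paragraph, "with an adjusted significance threshold set to alpha = 0.025 to accommodate multiple testing at the alpha = 0.05 level" for the litter and VSB strata. The calculation there is introduced by "Assuming two tailed two independent group comparisons", with "the size of each group N = 12", and states that the minimum effect "necessary to achieve statistical power P = 0.80 is d = 1.336".

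For GEE, mixed models and GLMs the SAP names no variance correction, no t or F reference, no df method, no GLM family and no dispersion estimator.

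**The concern.** Each contrast has 24 subjects, which is 24 clusters for GEE. Two features of large-sample inference make the test too liberal at that size. The uncorrected sandwich variance divides by n rather than n - 1, and a z reference ignores the uncertainty in the estimated variance. GEE in its standard form has both faults. A REML mixed model read against z has only the second.

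What is at stake is the protection the SAP sets up by splitting 0.05 over two contrasts. An analyst could follow a listed option to the letter, compare the p-value with 0.025, and run a false-positive risk per contrast that is clearly higher. The issue would remain if one of these methods were fixed in advance as the sole analysis, so it is separate from the number of options listed.

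**Working it through.** **Inputs.** From the SAP: 12 per group, two-sided 0.025 per contrast, power 0.80, d = 1.336, two contrasts and two time points. The contrasts use different subjects, so they are treated as independent. Assumed, because the documents are silent: the variance estimator, the reference distribution and the distribution of the outcome.

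**1. The plan's own figure.** Noncentral t, 22 df, two-sided 0.025, 12 per group: minimum d = 1.336, and power at d = 1.336 is 0.79997. A normal approximation would give d = 1.259. The stated figure therefore rests on a t test with 22 df.

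**2. GEE, uncorrected sandwich SE, z reference, normal change scores.** With complete data, an identity link and one value per time point, the group-by-time estimate is the difference in mean change. Its sandwich variance is (n - 1)/n = 11/12 of the t-test variance.
- Critical value: z(0.9875) = 2.2414.
- On the t scale: 2.2414 × √(11/12) = 2.146.
- Size: P(|t22| > 2.146) = 0.0432, or 0.0432/0.025 = 1.73 times nominal.
- Over two contrasts: 1 - (1 - 0.0432)² = 0.0845.
- Simulation of the same test gives 0.0433. Fitted GEE models in two separate runs gave 0.039 (3,000 fits) and 0.047 (1,500 fits).
- With 10 completers per group the values are 0.0476 and 0.0929; with 14, they are 0.0402 and 0.0788.

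**3. Mixed model, z reference.**
- REML: P(|t22| > 2.2414) = 0.0354; over two, 1 - (1 - 0.0354)² = 0.0696.
- ML: the variance factor is 22/24 = 11/12, so the result equals step 2.

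**4. GEE when change scores are skewed.** With assumed lognormal data, the default GEE test gives about 0.03 to 0.04 per contrast, with 0.029 at the strongly skewed end. The excess shrinks but stays above 0.025.

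**5. Gamma log-link GLM, Pearson scale, z reference.** This was simulated with an assumed log-scale SD, since the documents give none. Size is about 0.036 at SD 0.2, 0.052 at 0.75 and 0.065 at 1.0. Over two contrasts the ends are 1 - (1 - 0.036)² = 0.071 and 1 - (1 - 0.065)² = 0.126. A t reference reduces the excess but does not always remove it: 0.027 to 0.041 over three simulated distributions.

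**6. After correction.** The n - 1 variance with t on 22 df gives 0.025 (simulated 0.0251) and 1 - (1 - 0.025)² = 0.0494 over two. A Mancl-DeRouen SE gives 0.029 with z and 0.020 with t on 22 df. With strongly skewed lognormal change scores, the n - 1 variance with t gives about 0.014, so it errs on the safe side.

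**The case against.** The strongest reply is that the SAP never mentions z, Wald tests or an uncorrected sandwich variance, and names no software. Small-sample inference is as compatible with its wording as large-sample inference, and the power calculation is itself t-based. A reader might infer that the SAP prescribes tests that miss 0.025. The documents do not support that; they are silent on the choice. This stands, and it makes the finding conditional.

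A reader might also infer that GEE has to be removed because it brings nothing. That goes too far. A corrected variance with a t reference restores about 0.025. The identity between the GEE estimate and the difference in mean change needs complete data, an identity link and one value per time. Protocol section 5.1 takes four tape samples per subject at each sampling, and section 2.7 allows for attrition, so a clustered method could have a use.

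The sizes also depend on assumptions: 0.043 is for normal change scores, whereas the SAP expects non-normality, and the GLM values follow from an assumed log-scale SD. This is why ranges are given.

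Finally, it may be said that choosing a t test, ANCOVA or Mann-Whitney test makes the issue vanish, and that the SAP calls this a preliminary study. Both are true. But the SAP keeps the affected options open for its primary contrasts, offers the GLM as a remedy for a problem it expects, and sets a multiplicity-adjusted threshold. Silence therefore leaves a foreseeable route to a wrong error rate.

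**Conclusion.** The concern holds in conditional form. The SAP permits GEE, mixed models and non-linear-link GLMs for two contrasts of 12 versus 12 at 0.025, without a rule to keep inference valid at that size.

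| Option, if run with large-sample inference | Per contrast | Over two |
|---|---|---|
| GEE, uncorrected sandwich, z, normal change scores | 0.043 | 0.084 |
| GEE as above, assumed lognormal data | about 0.03 to 0.04 | – |
| REML mixed model, z, normal change scores | 0.035 | 0.070 |
| Gamma log-link GLM, Pearson scale, z, assumed log SD 0.2 to 1.0 | about 0.036 to 0.065 | about 0.071 to 0.126 |

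The first and third rows are exact under normality with 12 completers per group; the others are simulated under stated assumptions. Under normality, the change-score t test, the repeated-measures ANOVA and a REML mixed model with proper df hold 0.025. ANCOVA with its usual t or F reference should do so too, though it was not simulated. The gap is confined to the named options and should be closed before analysis.

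**What to change.** Add one sentence to the SAP requiring small-sample inference for the two primary contrasts, whichever listed option is used:

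- **GEE:** a bias-corrected (n - 1 type) sandwich variance with a t reference on 22 df. Alternatively, use the change-score t test, which has the same estimate with complete data, or ANCOVA.
- **Mixed model:** REML with Kenward-Roger or Satterthwaite df.
- **Non-linear-link GLM:** a permutation p-value, with the Mepilex label permuted within the body-fat strata used for randomisation (protocol section 5.1).

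The cost is that sentence and slightly less favourable p-values than large-sample output would show. Data collection and sample size do not change, and the stated d = 1.336 then matches the type of inference used.

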2 PARTICIPANTS

2.1) Participants. Describe the general characteristics of the subject populations or groups, including age range, gender, health status, and any other relevant characteristics.

Up to 84 subjects (non-military) will be recruited at the University of Washington (goal 72 subjects 12/group). Subjects will be randomly assigned to one of the six study groups. Characteristics described below.

- 2.2 Inclusion and exclusion criteria.
 - a. Inclusion criteria. Describe the specific criteria you will use to decide who will be included in your study from among interested or potential subjects. Define any technical terms in lay language.

Men and women aged 18 to 55 who meet the physical standards for military personnel and weigh less than 250 pounds (maximum allowable weight on the litter). Subjects must be able to remain in the study position for the duration of the study.

- b. Exclusion criteria. Describe the specific criteria you will use to decide who will be excluded from your study from subjects who meet the inclusion criteria listed above. Define any technical terms in lay language.
 - 1) previous injuries to sacrum/buttocks with scarring, 2) history of pressure injuries, 3) cardiovascular disease, 4) neurological disease that would affect vascular response, 5) diabetes, 6) history of malignancy, 7) current skin condition (e.g., eczema or psoriasis) which may interfere with the skin cytokine levels, 8) current neck/back pain or history of chronic neck/back pain, 9) known vertebral/spinal cord disease/injury (scoliosis, kyphosis, or lordosis), 10) self-reported pregnancy or 11) concern about their ability to remain in the vacuum spine board for 120 minutes. All subjects will be asked to refrain from the use of nonsteroidal anti-inflammatory medications for seven days before the experiment, to abstain from sun bathing for 24-hours before the experiment, to abstain from ingesting caffeine or smoking for six hours before the experiment, to avoid eating for 2 hours before the study (to increase accuracy of body fat measurement) and to not use any skin care products on the day of testing. Subjects will be informed of these requirements at the time of screening.
- **2.3) Prisoners**. IRB approval is required in order to include prisoners in research, even when prisoners are not an intended target population.
 - a. Will you recruit or obtain data from individuals that you know to be prisoners?

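### Holm's procedure over the two primary Mepilex contrasts would gain power on the fixed 0.025 threshold within the same 5% family-wise limit: an inexpensive improvement, not a correction of an error

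*SAP*

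**What the plan says.** The SAP's analysis text makes two within-platform comparisons primary: "the two contrasts LITTER + Mattress (Mepilex vs. not) and VSB (Mepilex vs. not) will be the analysis foci". Its power analysis rests on the IL-1α/total protein ratio; the other variables "will be treated as descriptive and secondary".

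For sample size, the SAP proceeds as follows: "Assuming two tailed two independent group comparisons", with "an adjusted significance threshold set to alpha = 0.025 to accommodate multiple testing at the alpha = 0.05 level" across the litter and VSB strata and "the size of each group N = 12". From this it concludes that "the minimum Cohen's d effect size per test necessary to achieve statistical power P = 0.80 is d = 1.336", and it concedes that an effect of that size is optimistic.

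The SAP names no step-down procedure and gives no power for showing both effects. It does not say whether success needs one contrast or both. The 0.025 appears only in the power section; the analysis text states no threshold.

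**The concern.** Read naturally, the power section describes plain Bonferroni: each contrast is judged at 0.025 whatever the other shows. That is valid but leaves part of the 5% allowance unused. If one platform is clearly positive and the other gives p = 0.03, the fixed rule calls the second platform negative, although a rule with the same family-wise limit would call it positive.

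This matters more than usual here because the groups are small and the detectable effect is large. With the group size settled at 12, the way alpha is spent is one of the few things that can still be improved without recruiting more subjects.

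**Working it through.** **Inputs from the documents**
- n = 12 per group, two-sided, two independent groups, 0.025 per contrast, d = 1.336, power 0.80 per test (SAP, Power Analysis).
- Two primary contrasts, each with its own control group. Protocol 2.1 states: "Subjects will be randomly assigned to one of the six study groups". No subject contributes to both contrasts, so the two test statistics are treated as independent.

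**Step 1. Reproduce the SAP's figure.** Two-sample t-test, noncentral t:
- degrees of freedom = 2 × 12 − 2 = 22; noncentrality = d × √(12/2) = 1.336 × 2.449 = 3.27.
- The d that gives 80% power at two-sided 0.025 is 1.336, and power at d = 1.336 is 79.997%. The stated figure reproduces.
- A normal approximation would give 84.9%, so the SAP used the t-based calculation.
- At two-sided 0.05 the same d has power 87.83%.

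**Step 2. Formulas.** Write a for power at 0.025 and b for power at 0.05, with equal effects on both platforms.
- Fixed rule: per contrast = a; both = a².
- Holm: a contrast is rejected if its p ≤ 0.025, or if its p lies between 0.025 and 0.05 and the other contrast has p ≤ 0.025. So per contrast = a + (b − a) × a.
- Holm rejects both if both p-values are ≤ 0.05 and they are not both above 0.025. So both = b² − (b − a)².
- At least one, under either rule = 1 − (1 − a)².

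**Step 3. At d = 1.336 on both platforms**
- Per contrast: fixed 0.800; Holm 0.79997 + 0.07837 × 0.79997 = 0.863.
- Both: fixed 0.79997² = 0.640; Holm 0.87834² − 0.07837² = 0.765. Simulation with 200,000 runs gave 0.638 and 0.764.
- At least one: 1 − 0.20003² = 0.960 under either rule.

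**Step 4. Other effect sizes**

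| True d (litter / VSB) | Per contrast, fixed | Per contrast, Holm | Both, fixed | Both, Holm |
|---|---|---|---|---|
| 1.0 / 1.0 | 52.7% | 59.1% | 27.8% | 40.6% |
| 1.336 / 1.336 | 80.0% | 86.3% | 64.0% | 76.5% |
| 1.6 / 1.6 | 92.6% | 96.0% | 85.8% | 92.5% |
| 1.336 on one, 1.0 on the other | – | – | 42.2% | 56.0% |

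If only one platform has an effect (d = 1.336), the other contrast clears 0.025 by chance 2.5% of the time. Holm then adds 0.07837 × 0.025 = 0.002, or about 0.2 points.

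**Step 5. Family-wise error**
- Both nulls true: 1 − 0.975² = 4.94% under either rule.
- One null true, d = 1.336 on the other platform: fixed 2.5%; Holm 0.025 + 0.025 × 0.800 = 4.5%. Simulation gave 2.46% and 4.46%.

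**The case against.** The strongest reply is that nothing in the plan is wrong. The SAP controls family-wise error validly, labels its power as per test, and gets the figure right. That stands: this is a choice between two valid procedures.

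A reader might infer from the 64.0% that the trial falls short of its 80% target. The documents do not support that. The SAP poses each platform as its own question and never requires both contrasts to be positive. On its own per-test measure, the gain at d = 1.336 is about 6 points. The 64.0% and 76.5% also need d = 1.336 on both platforms, which the SAP does not assume. The gain in joint power is smaller at larger effects (Step 4), and it nearly vanishes if only one platform responds.

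Two further objections stand in part:
- The fixed testing rule is inferred, because 0.025 is stated only for planning. If it was meant only for planning, the SAP has no decision rule for its two primary tests, and the same added sentence would supply one.
- The SAP leaves the primary test open (ANOVA, ANCOVA, change score, GEE or mixed models, transformation, Mann-Whitney), so the percentages above belong to a t-test only. Holm itself works on p-values and can be used with any of these.

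Nor is Holm entirely without cost. Simultaneous confidence intervals that match it are less simple, and the one-null error in Step 5 is higher than under the fixed rule, though within the limit.

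**Conclusion.** The point holds as an optional efficiency gain. Because Holm rejects whatever the fixed rule rejects, it cannot lose power, and it respects the 5% limit that the SAP chose. Under the planning effect on both platforms the gain is 6.3 points per contrast and 12.5 points for showing both. For scale, the fixed rule would reach joint power of 75.4% with 14 per group and 80.0% with 15.

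These sizes rest on a two-sample t-test, 12 analysed subjects per group, independent contrasts and the effect sizes named. They do not show that the SAP's 0.80 is mistaken or that the trial is underpowered by its own standard. The LiquiCell comparison lies outside this two-test family and is unaffected.

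**What to change.** Add one sentence to the SAP's analysis text: the two primary IL-1α/TP contrasts will be tested with Holm's procedure at a two-sided family-wise level of 0.05. Settle it before the data are examined. Leave 0.025 and d = 1.336 in the power section, since the smaller p-value still faces 0.025. If joint power is quoted, say that 76.5% assumes a t-test and d = 1.336 on both platforms.

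The change needs no extra subjects and no change of design. The team should also decide how it will present confidence intervals alongside Holm.
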